7.5.6 DLco sub-study

Subjects who participated in the DL_{CO} sub-study during the core study will be asked to continue their participation in the DL_{CO} sub-study during the extension study. The subjects may choose to continue participation by providing consent under a separate informed consent for the DL_{CO} substudy. The assessment will be conducted at visits indicated in Table 1 and Table 2. In addition, unscheduled DL_{CO} tests may be performed at any time during the study.

DL_{CO} tests will be performed by a PFT technician, respiratory therapist or expert or an equally experienced person according to the ATS/ERS guidelines [Miller 2005a]. DL_{CO} results will be reviewed by a pulmonologist or a physician adequately trained in pulmonology.

 DL_{CO} tests will be conducted according to the ATS/ERS guidelines and will be assessed by the single breath method [Macintyre 2005]. DL_{CO} efforts, up to a maximum of five, will be performed to produce at least two technically acceptable and repeatable traces (according to ATS/ERS guideline criteria). There must be a minimal interval of at least 4 minutes between each effort performed. Data from all DL_{CO} efforts collected during a session will be captured in the eCRF.

15 March 2022, page 99/216

EudraCT 2016-004719-10 EDMS-ERI-207656619

Confidential

The mean of two best within session DL_{CO} efforts will be selected and calculated by the sponsor as the value for this session. If only one acceptable effort is achieved, this will be selected by the sponsor for this session. If no acceptable effort is achieved, the effort with the highest inspiratory vital capacity will be selected by the sponsor for this session. For the analysis, the results will be corrected for hemoglobin (Hb) concentration and reported at a standard Hb concentration using the Cotes method [Macintyre 2005] (calculated by the sponsor in the database using the Hb value from the central laboratory).

The sites participating in the sub-study will use their own DL_{CO} gas analyzer and must ensure it is calibrated and working properly. The gas analyzer will need to fulfill the technical requirements and recommendations for range and accuracy for DL_{CO} assessment from the ATS/ERS guidelines [Macintyre 2005]. A copy of the calibrations of the day of a test must be stored as source documents in the subject charts at each subject visit, and a log of calibration results must be maintained at the site. In addition, frequent testing involving the same healthy subject control (biological quality check) or a DL_{CO} simulator will ensure continuous monitoring of the gas analyzer measurement accuracy over time.

If clinically significant alterations in DL_{CO} variables indicating a pulmonary condition that could result in increased risk for the subject are observed, she/he may be prematurely discontinued from the study treatment at the discretion of the investigator. Clinically relevant findings meeting the definition of an AE (new AE, or worsening of previously existing condition) [see Section 10.1], must be recorded on the AE page of the eCRF.

A back-up tester (PFT technician, respiratory therapist, or expert or an equally experienced person according to the ATS/ERS guidelines [Miller 2005a]) may conduct DL_{CO} if the primary tester is not available. This back-up tester must be trained on the specific requirements and have had refreshment on ATS/ERS recommendations before starting on the study. DL_{CO} conduct, documentation, performance, training details (of the responsible PFT site personnel), and quality control procedures are described in the PFT manual.

7.5.7 Ophthalmologic assessments

Ophthalmologic assessments will be performed at visits indicated in Table 1. In addition, unscheduled ophthalmological examination will be done in the event of visual symptoms or findings suggestive of active uveitis [see Section 5.1.12.7.1].

The safety ophthalmological assessment includes previous eye history and ophthalmic condition, any new or current ophthalmological symptoms, assessment of best corrected visual acuity (ETDRS charts), measurement of ocular pressure with Goldmann applanation tonometry (recommended, if not available other tonometry methods are allowed), slitlamp examination of the anterior segment, and dilated indirect funduscopy. Additionally, the safety ophthalmological assessment will include fluorescence angiography if there is a suspicion of active uveitis during the study (unless contra-indicated according to the ophthalmologist) [see Section 5.1.12.7]. While the visual acuity and ocular pressure measurement themselves may be performed by a delegate

15 March 2022, page 100/216

EudraCT 2016-004719-10 EDMS-ERI-207656619

Confidential

(e.g., technician, optometrician), the review and interpretation must be performed by the ophthalmologist. Conduct, review, and interpretation of all other ophthalmological exams must be performed by the ophthalmologist. Fluorescence angiography (if applicable) may be performed by a delegate (e.g., technician, optometrician) but always in the presence of the ophthalmologist who will review and interpret the results.

All parameters assessed at the ophthalmological examination should also be recorded in the eCRF as normal or abnormal. If an abnormality is found on any of the assessed parameters, it should be specified on the corresponding eCRF page. Clinically relevant findings meeting the definition of an AE (new AE, or worsening of previously existing condition) [see Section 10.1], must be recorded on the AE page of the eCRF.

7.5.8 Optical Coherence Tomography

OCT was assessed at visits indicated in Table 1 and Table 2 in Protocol Versions 1 to 5. The requirement for scheduled OCT assessments was removed from Protocol Version 6 onwards. Unscheduled OCT examination will have to be assessed in the event of visual symptoms or findings suggestive of macular edema according to the ophthalmologist's decision, or if active uveitis is diagnosed during the study [see Section 5.1.12.7]. While the OCT exam may be performed by a delegate (e.g., technician, optometrician), the review and interpretation must be performed by the ophthalmologist.

All examinations will be documented in the source documents of the subject. OCT examination should also be recorded in the eCRF as normal or abnormal. If an abnormality is found, it should be specified on the corresponding eCRF page. Clinically relevant findings meeting the definition of an AE (new AE, or worsening of previously existing condition) [see Section 10.1], must be recorded on the AE page of the eCRF.

7.5.9 Weight

Body weight will be measured at visits indicated in Table 1. In addition, unscheduled body weight measurement may be performed at any time during the study. Data will be collected in the eCRF.

7.5.10 Physical examination

Physical examination is performed by the principal investigator or treating neurologist at visit indicated in Table 1 and Table 2. In addition, unscheduled physical examination may be performed at any time during the study.

Physical examination includes the examination of the general appearance, head, eyes, ears, nose, throat, neck, heart, lungs, abdomen, lymph nodes, extremities, skin, neurological and musculoskeletal functions. Other exams will be performed if indicated, based on medical history and/or symptoms.

15 March 2022, page 101/216

Confidential

EudraCT 2016-004719-10 EDMS-ERI-207656619

Information for all physical examinations must be included in the source documentation at the study site. The observations should be reported by body system in the eCRF as normal or abnormal. If an abnormality is found, it should be specified on the corresponding eCRF page, describing the signs related to the abnormality (e.g., systolic murmur). Clinically relevant findings meeting the definition of an AE (new AE, or worsening of previously existing condition) must be recorded on the AE page of the eCRF.

Note:

The standardized neurological evaluation based on EDSS and FS scores conducted by the efficacy assessor [see Section 7.4.1] does not obviate the requirement for the examination of the neurological function as part of the physical examination by the treating neurologist.

7.5.11 Dermatological examination

A complete skin examination will be performed by a dermatologist at visits indicated in Table 1 and Table 2. In addition, unscheduled complete skin examination may be performed by the dermatologist at any time during the study, if indicated.

In the event of findings of suspicious or pre-cancerous or cancerous skin disorders observed at any visit during the study, the dermatologist will conduct further examination, as per local standard practice, including the taking of skin biopsies if required to rule out or confirm a diagnosis.

All examinations will be documented in the source documents of the subject. Dermatological examination should be recorded in the eCRF as normal or abnormal. If an abnormality is found, it should be specified on the corresponding eCRF page. Clinically relevant findings meeting the definition of an AE (new AE, or worsening of previously existing condition) [see Section 10.1] will be recorded accordingly on the AE page of the eCRF.

7.5.12 Laboratory assessments

7.5.12.1 Type of laboratory

A central laboratory (see central laboratory manual for contact details) will be used for all protocol-mandated laboratory tests, including re-tests due to laboratory abnormalities and laboratory tests performed at unscheduled visits. Central laboratory data will be automatically transferred from the central laboratory database to the sponsor's clinical database.

Under specific circumstances, laboratory samples could be drawn in a local laboratory close to where the subject lives and analyzed at the central laboratory. In such circumstances, the local laboratory must be provided with the central laboratory kits, which must be used for blood collection. The blood samples collected locally will be shipped by the local laboratory to the central laboratory for analysis. Such a local laboratory shall be identified as soon as possible, but no later than upon enrollment of the subject in the study.

Local laboratory results will only be collected in exceptional cases (e.g., subject is hospitalized in a different hospital from the study center due to a medical emergency). In cases where a local

15 March 2022, page 102/216

Confidential

EudraCT 2016-004719-10 EDMS-ERI-207656619

laboratory is used for the collection and analysis of blood samples, the local laboratory results (with the corresponding normal ranges) will be entered into the clinical database via dedicated eCRF pages.

If a central laboratory sample is lost, has deteriorated or cannot be analyzed for whatever reason, the investigator will collect an additional sample as soon as possible for repeat analysis if still clinically relevant.

The central laboratory will provide all laboratory results by fax or normal mail to the site. Any alerts will be indicated on the report [see Section 5.1.12].

- Teriflunomide plasma concentration: A plasma sample will be taken on Day 1 for a teriflunomide test (results to be communicated to site only if needed, e.g., in the case of AEs where the measurement of exposure to teriflunomide is of relevance).
- Important note: Additional teriflunomide testing is no longer required with the approval of protocol version 5. Under protocol versions 1 to 4, teriflunomide plasma concentration may be assessed at Week 19 ± 7 days and at Week 21 ± 7 days and may be repeated at Visit 5 (Week 24) and at following visits if necessary until two consecutive test results confirming plasma concentration of teriflunomide <0.02 mg/L are available.

All laboratory reports must be signed and dated by the principal investigator or delegate within 5 calendar days of receipt and filed with the source documentation. The investigator/delegate must indicate on the laboratory report whether abnormal values are considered clinically relevant or not. Clinically relevant laboratory findings meeting the definition of an AE [see Section 10.1] must be reported as an AE or SAE as appropriate, and must be followed until the value returns to within the normal range or is stable, or until the change is no longer clinically relevant. Further laboratory analyses should be performed as indicated and according to the judgment of the investigator.

Details about the collection, sampling, storage, shipment procedures, and reporting of results and abnormal findings can be found in the laboratory manual.

7.5.12.2 Laboratory tests

Blood samples will be drawn when applicable, before the morning administration of study medication visits indicated in Table 1. Fasting conditions are recommended but not required. Unscheduled laboratory tests may be performed at any time during the study.

Urinalysis will be assessed using dipsticks at visits indicated in Table 1 and Table 2. In addition, unscheduled urinalysis may be performed at any time during the study.

Hematology

- Red blood cell count
- Total and differential white blood cell counts (basophils, eosinophils, lymphocytes, monocytes, neutrophils, band forms)

Confidential

Platelet count

15 March 2022, page 103/216

- Hb
- Hematocrit

Clinical chemistry

- Glucose
- ALT, AST, AP, total bilirubin, lactate dehydrogenase
- International Normalized Ratio
- Creatinine
- Calculated creatinine clearance (Cockroft-Gault)
- Urea
- Uric acid
- Total cholesterol
- Triglycerides
- Sodium, potassium, chloride, calcium
- Total protein, albumin
- C-reactive protein

Biomarkers and additional analyses in the event of infections

• A serum sample will be taken at Visit 1 to be stored at the central laboratory for potential retrospective analyses of viral serology titers in the event of infections (e.g., suspected opportunistic infection) during the study and for analysis of biomarkers.

Immunogenicity evaluations

• At every scheduled visit after approval of protocol version 5, a 5 mL serum sample will be taken for immunogenicity evaluations (e.g., anti-SARS-CoV-2 antibody titers, SARS-CoV-2 neutralization assays).

Pregnancy test

A serum and urine pregnancy tests for WOCBP and will be performed at visits indicated in Table 1 and Table 2 and if pregnancy is suspected during the study. Additionally, urine pregnancy tests will be performed at home every 4 weeks (±7 days) between the visits. Subjects will communicate the result (telephone call) of the tests to the principal investigator / treating neurologist.

Female subjects who interrupt the study treatment because of planned pregnancy will be exempted from any protocol-mandated pregnancy tests after the first positive pregnancy test and until 30 days before study drug re-initiation.

15 March 2022, page 104/216

Confidential

EudraCT 2016-004719-10 EDMS-ERI-207656619

Serum pregnancy testing results will be automatically transferred from the central laboratory database to the sponsor's clinical database. Urine pregnancy testing results will be recorded in the eCRF. In the event of pregnancy, a Pregnancy Form must be completed [see Section 10.3].

Urinalysis

- pH
- Glucose
- Proteins
- Blood
- Leukocytes
- Bilirubin, urobilinogen

Urine dipsticks provided by the central laboratory will be used to perform the urinalysis. The test should be performed and analyzed at the site. The results must be documented in the source documents / subject charts and should be recorded in the eCRF as normal or abnormal. If an abnormality is found, it should be specified on the corresponding eCRF page and the results for the abnormal parameter will be reported in the eCRF. Clinically relevant findings meeting the definition of an AE (new AE, or worsening of previously existing condition) [see Section 10.1] will be recorded accordingly on the AE page of the eCRF.

Teriflunomide plasma level tests:

The results of the teriflunomide test conducted with the plasma sample taken on Day 1 will be communicated to site only if needed, e.g., in the case of AEs where the measurement of exposure to teriflunomide is of relevance.

During the early stages of the study (protocol versions 1 through 4), additional plasma teriflunomide tests may have been required to confirm that teriflunomide plasma levels were sufficiently low (<0.02 mg/L) before fertile male participants could stop contraceptive requirements and in the case of planned pregnancies (see Section 5.1.12.5). Following approval of protocol version 5, these tests are no longer required now that all ongoing subjects have been off teriflunomide for over 2 years (last subject entered this extension study on 20-May-2019) [Aubagio® USPI, Aubagio® SmPC].

The plasma teriflunomide concentration will be determined by using a high-performance liquid chromatography method [Sobhani 2010].

7.6 Electronic self-rated version of the Columbia-Suicide Severity Rating Scale

The electronic self-rated version of the Columbia-Suicide Severity Rating Scale (eC-SSRS) is used to reliably and consistently monitor subjects for suicidal ideation and behavior during the study. It will be completed at visits indicated in Table 1 and Table 2.

15 March 2022, page 105/216

EudraCT 2016-004719-10 EDMS-ERI-207656619

Confidential

The eC-SSRS assesses lifetime suicidality during an initial baseline evaluation, and then prospectively monitors ideations and behaviors at subsequent follow-up assessments. At each visit the eC-SSRS is completed, the treating neurologist will review the responses provided by the subject and assess the findings. The eC-SSRS is a fully structured clinical interview designed and developed for electronic administration. Subjects will be asked to respond to standardized clinical questions aimed at measuring the severity of suicidal ideation (rated on a 5-point ordinal scale), the levels of suicidal behavior, and the category self-injurious behavior without suicidal intent. Any subjects who reaches an eC-SSRS suicidal ideation score of 4 or above, or who responds "yes" on the eC-SSRS suicidal behavior item must be referred to an appropriate health professional who should make a decision on the management of the suicidal symptoms and recommend whether or not the subject should continue the treatment with the study drug.

It is recommended that the eC-SSRS is completed prior to any clinical assessments, and after the SF-36v2TM has been completed. Preferably, subjects would complete the eC-SSRS while waiting for their appointment before any interaction with health care providers.

The clinical site will provide either a telephone, tablet, or computer for the subject to complete the eC-SSRS. A sample of the telephone administered eC-SSRS (in English) is provided as Appendix 8. The data will be collected by a vendor who will send the results to the sponsor.

In exceptional cases only (e.g., problem with the server), a clinician administered C-SSRS (paper version) may be administered by an adequately qualified and trained clinician. The clinician administered C-SSRS (paper version) does not need to be recorded in the eCRF. However, any subject who reaches a C-SSRS suicidal ideation score of 4 or above, or who responds "yes" on the C-SSRS suicidal behavior item must be referred to an appropriate health professional, as described above. Furthermore, an eC-SSRS should be completed at the next applicable visit (provided the reason for conducting a paper C-SSRS is no longer applicable).

The sponsor has been granted a license agreement for the use of the eC-SSRS and the clinician administered C-SSRS (paper version).

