Other endpoints		
 Absolute values and change from baseline for HR, SBP, DBP and body weight at all assessments 	Y	Y
• Treatment-emergent notable blood pressure abnormalities##	Y	Y
 Absolute values and change from baseline for laboratory tests (hematology, blood chemistry, urinalysis) at all assessments 	Y	Y
• Treatment-emergent notable laboratory abnormalities##	Y	Y
 Change from baseline to EOS versus change from baseline to EOT in lymphocyte counts (absolute and percent change)** 	Y	N
• Treatment-emergent eC-SSRS suicidal ideation score of 4 or above, or a "yes" response on the eC-SSRS suicidal behavior item	Y	N

Cumulative safety data, i.e., AEs for the combined analysis period will only be presented for subjects who received 20 mg ponesimod in the core study.

The selection of AEs of special interest [see Appendix 4] is based on the anticipated risks of treatment with ponesimod; the final list of AEs of special interest will be defined in the SAP.

The selection of notable abnormalities considered for the analyses is based on standard definitions and the anticipated risks of treatment with ponesimod; the final list of abnormalities will be defined in the SAP.

^{**} Only for subjects who have no exposure to commercially available ponesimod prior to the EOS visit.

AE = adverse event; DBP = diastolic blood pressure; DL_{CO} = diffusing capacity for the lungs measured using carbon monoxide; eC-SSRS = electronic self-rated version of the Columbia-Suicide Severity Rating Scale; ECG = electrocardiogram; EOS = End-of-Study; EOT = End-of-Treatment; FEV_1 = forced expiratory volume in 1 second; FVC = forced vital capacity; HR = heart rate; QTcB = QT corrected for heart rate on the basis of Bazett's formula; QTcF = QT corrected for heart rate on the basis of Fridericia's formula; SAE = serious adverse event; SAP = statistical analysis plan; SBP = systolic blood pressure.

15 March 2022, page 89/216

Confidential

EudraCT 2016-004719-10 EDMS-ERI-207656619

The treatment-emergent period is defined as the time from first ponesimod administration in the applicable Analysis Period up to 15 days (inclusive) after last study treatment administration. This definition applies regardless of whether the subject receives commercially available ponesimod after completing study treatment.

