11.4.8.5 Laboratory endpoints

Descriptive summary statistics by visit will be provided for observed treatment-emergent values and absolute change from core baseline for laboratory tests (hematology, blood chemistry, urinalysis) by core study treatment for the Combined Analysis Period using the SAF. These parameters will also be summarized descriptively for the Extension Analysis Period by core study treatment and overall using the EXTS.

Treatment-emergent laboratory notable abnormalities will be summarized for subjects who received ponesimod 20 mg in the core study only for the Combined Analysis Period using the SAF.

The definition for notable abnormalities is provided in Appendix 5 and include:

- Treatment-emergent laboratory test abnormalities based on normal ranges of the central laboratory, project-specific ranges, and common terminology criteria for adverse events (CTCAE) [CTCAE 2010; see Appendix 5]
- Treatment-emergent laboratory test abnormalities based on FDA guidance for DILI [FDA 2009b] (for ALT / AST / total bilirubin).

Lymphocyte count reversibility after EOT will be summarized descriptively by comparing the mean (and 95% CIs) for absolute change in lymphocyte counts from core baseline to EOS, and from core baseline to EOT.** This analysis will be performed for the Combined Analysis Period by core study treatment using the SAF.

** applies only to subjects who have no exposure to commercially available ponesimod prior to the EOS visit.

11.4.8.6 eC-SSRS

The number and percentage of subjects with a treatment-emergent eC-SSRS suicidal ideation score of 4 or above, or a "yes" response on the eC-SSRS suicidal behavior item will be summarized descriptively by core study treatment for the Combined Analysis Period.

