12.3 Database management and quality control

Electronic CRFs will be used for all subjects. The investigator will have access to the site eCRF data until the database is locked. Thereafter, they will have read-only access. The eCRF must be kept current to reflect subject status at any timepoint during the course of the study.

While entering the data, the investigator/delegate will be instantly alerted to data queries by validated programmed checks. Additional data review will be performed by the sponsor on an ongoing basis to look for unexpected patterns in data and study monitoring. If discrepant data are detected, a query specifying the problem and requesting clarification will be issued and visible to the investigator/delegate via the eCRF. All electronic queries visible in the system either require a data correction (when applicable) and a response from the investigator/delegate to clarify the queried data directly in the eCRF, or simply a data correction in the eCRF. The investigator/delegate must, on request, supply the sponsor with any required background data from the study documentation or clinical records. This is particularly important when errors in data transcription are suspected. In the case of health authority queries, it is also necessary to have access to the complete study records, provided that subject confidentiality is protected.

This process will continue until database closure.

Laboratory samples, ECGs, SF-36v2TM,eC-SSRS assessments will be processed through a central laboratory/provider and the results will be sent electronically to the sponsor. Any data received from central laboratory or central ECG facility generated in relation to follow up on adverse events which are ongoing at end of study should be entered in the database even if obtained after the EOS visit.

15 March 2022, page 146/216

Confidential

EudraCT 2016-004719-10 EDMS-ERI-207656619

After the database has been declared complete and accurate, the database will be closed. Any changes to the database after that time may only be made as described in the appropriate SOP. After database closure, the investigator will receive the eCRFs of the subjects of her/his site (including all data changes made) on electronic media or as a paper copy.

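### The fallback paper C-SSRS is exempt from eCRF entry, so a positive paper result reaches the suicidality endpoint only if the subject reports the event again on a later eC-SSRS

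*Protocol*

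**What the plan says.** - **Fallback.** Section 7.6: "In exceptional cases only (e.g., problem with the server), a clinician administered C-SSRS (paper version) may be administered". This paper form "does not need to be recorded in the eCRF".
- **Threshold.** The same section requires referral to a health professional for "any subject who reaches a C-SSRS suicidal ideation score of 4 or above", or for a positive answer on the behavior item. This matches the rule for the electronic form.
- **Repeat.** Section 7.6 also asks for an eC-SSRS at the next applicable visit, once the reason for using paper no longer applies.
- **Endpoint.** Table 9 (Section 6.2) lists "Treatment-emergent eC-SSRS suicidal ideation score of 4 or above", or a positive behavior item, for the Combined Analysis Period and not for the Extension Analysis Period. Section 11.4.8.6 plans "The number and percentage of subjects with a treatment-emergent eC-SSRS suicidal ideation score of 4 or above" or a positive behavior item, by core study treatment.
- **Data route.** For the electronic form, Section 7.6 says: "The data will be collected by a vendor who will send the results to the sponsor". Section 12.3 agrees: "eC-SSRS assessments will be processed through a central laboratory/provider and the results will be sent electronically to the sponsor". No route is described for the paper form.

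**The concern.** A result serious enough to require referral need not enter the database, and the endpoint built on that same threshold is worded so that it would not count it. Electronic results come from the vendor and the paper result stays at the site.

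This is a stated rule, not detail left to the SAP: an analysis plan cannot summarize data that the protocol exempts from collection. It also differs from how the protocol treats comparable data. The SDMT paper form is transcribed into the eCRF (Section 7.4.5), and local laboratory results that replace central ones go into dedicated eCRF pages (Section 7.5.12.1). No reason is given for treating the C-SSRS differently.

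The endpoint is a count of rare, serious events. A paper negative that is not entered leaves that count unchanged. A paper positive that is not entered and not reported again lowers it. The error therefore has only one direction.

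**Working it through.** The plan gives no figure for this endpoint, so there is nothing to reproduce. The check traces a positive paper result through the schedule and then sizes one lost case.

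**1. When a later eC-SSRS can recover the event**

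- Table 1 and Sections 8.3.9-8.3.10 schedule the eC-SSRS at Weeks 48, 96, 144 and 192 and at EOT.
- A subject who stays on treatment after a paper form at one of the first four visits has the next scheduled electronic form up to 48 weeks later. Appendix 8 asks about the whole period since the previous electronic call, so that form spans the failed visit. Recovery then depends on self-report over that interval.
- A subject who stops treatment early has an EOT visit no later than 14 days after the last dose (Section 3.2.3.1; Table 1, note 14). The EOT list includes the eC-SSRS. An EOT form completed by then falls inside the treatment-emergent period, which closes 15 days after the last dose (Section 6.2).

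**2. When it cannot**

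- *Paper form at EOT, not repeated within the visit window.* The eC-SSRS is not in the End-of-Study (EOS) list (Section 8.4.1), in Table 2, or in the list for unscheduled visits (Section 8.5.2). EOS is 30-44 days after the last dose, so even an ad hoc form there would fall after day 15.
- *Withdrawal of consent.* No further eCRF data are collected, and findings at a last contact stay in the medical records (Section 9.2).
- *Loss to follow-up or death* before the next electronic form.
- *Non-report.* The later form is completed but the subject does not report the event again.

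**3. Size of one lost case**

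The endpoint belongs to the Combined Analysis Period, for which safety analyses use the Safety Set: everyone who received core study treatment (Sections 11.2.3, 11.2.6). Inputs: N = 1100 planned in the core study (Section 11.6); true rate r = 0.5-1% (assumption; the protocol gives none).

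- Expected positives = N × r = 1100 × 0.005 = 5.5 to 1100 × 0.01 = 11.
- One lost case as a share of the total = 1/11 = 9% to 1/5.5 = 18%.
- Results are shown by core treatment. With about half the subjects in each group (Section 5.1.7), 550 × r = 2.75-5.5 positives per group, and one lost case is 1/5.5 = 18% to 1/2.75 = 36% of that group's count.

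**4. Expected loss**

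Let p be the share of assessments done on paper. The protocol gives no figure; take p = 1-5% as an assumption, and suppose positives are no more likely than negatives to fall on paper. Before any recovery under step 1, the expected loss is at most p × positives: 0.01 × 5.5 = 0.06 to 0.05 × 11 = 0.55 cases. Recovery reduces this further.

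**The case against.** The strongest reply is that the protocol already has a safety net, and much of that stands.

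- *Leaving treatment triggers an eC-SSRS.* A reader might infer that subjects with a positive paper form, once referred, tend to leave before the next electronic form, so that losses concentrate among positives. The documents do not support that: premature discontinuation itself brings an EOT visit with an eC-SSRS. Only withdrawal from all participation, loss to follow-up, death or a missed EOT escapes.
- *A paper positive is not barred from counting.* The exemption is permissive, and the later form's recall period covers the event. But even if a site did enter the paper score, the endpoint as worded would not count it.
- *A paper form at EOT is not necessarily lost.* Section 8.3.10 lets other EOT assessments be done within the visit window, and the form can be completed by telephone, tablet or computer. A brief server fault could be made good, provided the repeat falls within 15 days of the last dose.
- *The event can reach the database as an adverse event* if clinically significant (Section 10.1.1), and referral protects the subject either way. That is true, but it does not feed this endpoint.
- *The SAP defines safety variables* (Section 11.3.3). It can decide whether to pool the two versions, but only if the paper data have been collected.

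**Conclusion.** The point holds as a minor data-capture gap. As written, a threshold-positive paper result counts only through a second report on a later eC-SSRS. That form is usually available, but not always, and any loss can only reduce the count.

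One lost case would be about 9-18% of the total count, given 1100 treated subjects and the assumed 0.5-1% rate. That is the weight of a case if one is lost, not a forecast that one will be. Paper use is restricted to exceptional circumstances, its frequency is not stated, and under the illustrative 1-5% paper share the expected loss is at most 0.06-0.55 cases before recovery. It would also be wrong to size this on the roughly 800 subjects expected in the extension. They are the ones exposed to this rule, but the endpoint is summarized on the Safety Set.

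The documents do not support reading this as a large or systematic understatement of suicidality, or as a threat to subject safety.

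**What to change.** - **Section 7.6:** replace the exemption with a requirement to enter the paper C-SSRS ideation score and behavior item in the eCRF.
- **Table 9 and Section 11.4.8.6:** count a subject as positive on either version, flag the version in the listing, and also show the count based on the eC-SSRS alone.

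The referral rule stays as it is and no assessment is added. The cost is one eCRF page and a sentence in the analysis text; the form is already completed by a trained clinician. The one downside is a small mix of clinician-rated and self-rated results, which the flag and the eC-SSRS-only count make visible. Paper forms already completed could be entered retrospectively where sites still hold them.
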